The prescribing of inappropriate medications for older adults is extremely common in the United States, ranging from 12% in community settings to 40% of those who are institutionalized.¹⁻³ Benzodiazepines, anticholinergics, and sedative hypnotics are among the most commonly prescribed in circumstances that are inconsistent with practice guidelines.^{3,4} While inappropriate prescribing increases the risk of adverse health consequences for all patients, older adults are particularly vulnerable.^{2,5-7} Physicians' lack of awareness of alternatives, ambiguous practice guidelines, and perceived pressure of patients or caregivers are among the reasons why these drugs are used more than might be optimal.²

Reducing inappropriate use of these drugs may be achieved through decision support tools for physicians that are embedded in electronic health record (EHR) systems. While EHR strategies are widely used to support the informational needs of providers, these tools have demonstrated only modest effectiveness at improving prescribing.⁸⁻¹³ The moderate effectiveness of current clinical decision support tools is thought to be largely due to what content they contain and the lack of provider-focused design principles being used to develop them.^{14,15} Prior approaches have also been criticized for the sheer volume of alerts, the lack of clinical significance of the tools, and the poor/delayed timing of the clinical decision support (i.e., after the prescribing decision). Accordingly, the effectiveness of these tools could be enhanced by leveraging recently-gained insights from behavioral economics and other related sciences. Their application to EHRs has been limited, and they have not been used to reduce the prescribing of potentially harmful medications to older adults.

2. Study Aims

The overall goal of the proposed research is to evaluate whether EHR-based tools, optimized using behavioral science principles, reduce inappropriate prescribing among older adults. Our overall hypothesis is that thoughtful incorporation of behavioral principles into

EHRs will reduce inappropriate prescribing and adverse drug events among older adults compared to usual care.

The objectives and endpoints for the adaptive and replication trials are summarized below.

OBJECTIVES	ENDPOINTS	JUSTIFICATION FOR ENDPOINTS
Primary		
To determine whether EHR-tools designed using behavioral science principles are more effective than at reducing inappropriate prescribing of high-risk medications in older adults than standard EHR tools or usual care.	Composite of 1) discontinuation of high-risk medications (benzodiazepines, sedative hypnotics, or anticholinergics) or 2) ordering a gradual dose taper for one of these medications	These outcomes are rapidly measurable using EHR data alone and will provide evidence of provider behavior change.
Secondary		
To examine whether behavioral science-based EHR tools reduce cumulative prescribing of high-risk medications in older adults compared with usual care.	Quantity of high-risk medication prescribed, defined by number of pills and milligram equivalents of high-risk medications prescribed to patients in follow-up	These outcomes capture the extent to which high-risk medications are cumulatively prescribed to patients by all providers over the follow-up period.
Tertiary/Exploratory		
To evaluate whether behavioral science-based EHR tools reduce the risk of clinically-significant adverse drug events, falls, fractures, hospitalizations, or emergency room visits compared with usual care.	Rates of adverse drug events, falls, fractures, hospitalizations, and emergency room visits in follow-up; quantity of high-risk medications dispensed to patients in follow-up period	These outcomes measure clinical outcomes that are consequences of these high-risk medications, measured in medical and pharmacy administrative claims data.

3. Study Design

3.1 Study site

The replication trial will be conducted in outpatient primary care practices at Mass General Brigham (MGB), specifically Mass General Hospital. MGB has a fully functional EHR, EpicCare (www.epicsys.com), that supports computerized ordering of medications. MGB is comprised of 150 outpatient practices with over 1,800 physicians.

3.2 Overall design

We will conduct a parallel group trial at Mass General Brigham, specifically within MGH primary care practices. We hypothesize that these tools will reduce prescribing of high-risk medications (primary outcome), cumulative prescribing of high-risk medications (secondary outcome), and clinically-significant adverse drug events like sedation and confusion (tertiary outcome) compared with usual care.

3.2.1 *Trial Design*

[figure not shown]
This trial is a cluster-randomized, NIH-defined Phase III pragmatic trial. The study statistician, in partnership with data analysts at MGB, will generate and implement the randomization scheme, with oversight by the Principal Investigators. All the study sites will be at MGH for this trial; we have received approval from leadership at MGH primary care practices and Digital Health eCare teams to conduct this trial. For study evaluation, data regarding patients' medical history, disease control, medication use, and healthcare utilization will be obtained from EHR data or administrative claims data. Any administrative claims data used for evaluation in this study will come directly from MGB in HIPAA-limited datasets through their risk-bearing contracts.

We will randomize primary care providers at MGH to one of the 2 most promising treatment arms identified in the prior adaptive randomized trial conducted at Atrius Health or usual care (described in further detail in 5.2). We expect to randomize approximately 200 providers. Providers randomized to one of the 2 selected treatment arms will receive an EHR tool to guide their care of eligible patients. We will randomize providers based on provider demographic characteristics, patient case-mix factors, and baseline rates of high-risk medication prescribing measured in EHR data.

Providers will be eligible if they prescribed a benzodiazepine, sedative hypnotic, or two distinct anticholinergics to at least one older adult in the 180 days prior to randomization. Providers will receive these EHR tools for their patients who meet the following criteria: 1) older adults (aged 65 years or more), and 2) who have been prescribed at least 90 pills of benzodiazepine or sedative hypnotic or have been prescribed at least one active orders of at least 90 pills of two different anticholinergics in the last 180 days. Follow-up will last 12 months. These patients will also be included in the analyses. The type and timing of EHR tool that the providers receive for these patients will vary based on their assigned intervention arm.

3.3 Study Schema

3.3.1 *Mass General Brigham*

3.4 Scientific rationale for study design

The use of a randomized trial in this setting is scientifically justified, as this design will be able to provide evidence of causality in the effectiveness of the tools on reducing prescribing and rates of clinical outcomes. An observational study design, by contrast, would not provide the same degree of scientific rigor.

3.5 Justification for intervention

The focus areas for the EHR tools will be primarily drawn from the outpatient Choosing Wisely recommendations in geriatric medicine but are also informed by the Beers Criteria and

other major clinical guidelines.¹⁶⁻¹⁸ In specific, we plan to focus on the following therapeutic classes: (1) benzodiazepines; (2) sedative hypnotics (sleep medicines) and (3) anticholinergics. These classes were chosen because they all have established clinical guidelines recommending reductions in use, continue to be heavily over-prescribed, contribute significantly to poor clinical outcomes in older adults, and also have non-drug or less risky therapeutic alternatives. While prescribing non-drug options may be the optimal alternative to these potentially inappropriate medications, their adverse effects could also be attenuated by choosing alternative medications in a different drug class, lower doses of medication, or alternative, safer medications within the same drug class.

We have chosen to focus on key principles of behavioral economics and cognitive psychology to “nudge” providers to optimize prescribing, such as timing, salience, framing, simplification, pre-commitment, and boosting. These principles were selected based on their effectiveness in other settings¹⁹⁻²², their applicability to the care of older adults, and their ability to be adapted to the EHR context.

3.6 End-of-study definition

The MGB trial will be completed 12 months after randomization. Providers and their eligible patients will be followed until the end of this follow-up date, or until censoring.

3.7 Data sources

We will use EHR data to implement the EHR tools, identify study subjects, track study progress, and evaluate the effect of the interventions. We will also use administrative claims data to evaluate tertiary outcomes among the subgroup of patients with claims data.

Data warehouses reside in an Oracle environment and consist of the Clarity and Payer databases. The Clarity database is a relational database that contains clinical and financial information from the Epic Suite of products; including the electronic medical record system, the

appointment scheduling system, the patient accounting system, and the master patient index (Identity). The various tables within the Clarity database are refreshed on a daily, weekly or monthly basis. At MGB, we will extract clinical information from the electronic medical record system via the Epic Enterprise Data Warehouse (EDW) or the Mass General Brigham Research Patient Data Registry (RPDR). Accessing the EDW in particular is necessary in order to adequately identify and link all eligible patients seen by the enrolled providers in our study and measure outcomes, which is not possible using other sources.

For the claims data, the Medicare claims data are being provided by the funder, the National Institute on Aging (NIA), through their partnership with Acumen and the established MedRIC (<https://www.medric.info/data-enclave/data-pages/data>). In order to obtain claims data from the funder, we will provide them with Medicare Beneficiary Identifier (MBI) for linked patients in our study. We are executing all appropriate data use agreements with the NIA and Acumen to receive these data.

3.8 Schedule of activities

Data collection	MGB trial: Pre-randomization	MGB trial: Follow-up
EHR review for provider eligibility	X	
Patient characteristics (Demographics, clinical characteristics)	X	
Provider characteristics (Demographics, patient case-mix)	X	
Benzodiazepine/sedative hypnotic prescribing		X
Benzodiazepine/sedative hypnotic dispensations		X
Anticholinergic prescribing/dispensations		X
Adverse drug events		X
Falls or fractures		X
Resource use (hospitalizations, ER visits)		X

4. Study Population

The study will intervene upon primary care providers (primary care provider designated physicians, nurse practitioners, physician assistants) and their patients in the outpatient practices of Mass General Hospital.

4.1 Inclusion Criteria

The subjects involved in this trial are providers from multiple clinical sites, all at Mass General Hospital. The target population of providers and the patients they treat is pragmatic and widely representative. Providers will be eligible if they treat older adult patients. Each study clinic has an EHR system in place. The inclusion criteria are limited to maximize generalizability in accordance with pragmatic trial principles by PRECIS-2 (PRagmatic Explanatory Continuum Indicator Summary).

Providers will be eligible if they:

- Are a primary care provider at Mass General Hospital, with a minimum clinical schedule of 2 sessions per week
- Prescribed a benzodiazepine, sedative hypnotic, or anticholinergic to at least one older adult in the 180 days prior to randomization

Patients will be included in the analysis if they:

- Are assigned to one of the randomized primary care providers (by MGB indicators)
- Are aged 65 years or more
- Have been prescribed at least 90 pills of benzodiazepine or sedative hypnotic or at least one active orders of at least 90 pills of two different anticholinergics in the prior 180 days

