4.2 Exclusion Criteria

Patients not meeting the inclusion criteria above will not be included in the study. No other exclusion criteria will be used.

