6.2 Outcomes

The primary outcome will be a binary composite measure of a reduction in inappropriate prescribing, evaluated using EHR data. In specific, we will measure a composite of 1) discontinuation of high-risk medications (benzodiazepines, sedative hypnotics, or anticholinergics) defined by either: a) active discontinuation and no subsequent order or b) no order during follow-up or 2) ordering a gradual dose taper (for benzodiazepine or sedative hypnotics). Our primary analyses will be within patients who had a visit (telemedicine or in-person) with a study provider after randomization. If either of these actions is taken by providers for a specific patient at any point in the follow-up window, we will classify the patient as having had a reduction in inappropriate prescribing. If the patient has multiple therapeutic classes of interest (e.g., benzodiazepines and sedative hypnotics), we will classify patients with a reduction for any class as a “reduction” for the composite measure. We will also stratify

patients by their number of eligible therapeutic classes (i.e., one, two, or three classes) and analyze outcomes within these strata.

Secondary outcomes include the quantity of high-risk medication prescribed, defined by number of pills of high-risk medications (all three classes) prescribed to patients in the follow-up period and number of lorazepam milligram equivalents of benzodiazepines and sedative hypnotics to capture cumulative prescribing by all providers. As above, we will also stratify patients by their number of eligible therapeutic classes (i.e., one, two, or three classes) and analyze outcomes within these strata.

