7.3 Statistical analyses

7.3.1 *Analysis of the primary endpoints*

The unit of analysis is at the patient-level. All analyses will use intention-to-treat principles. We will use generalized estimating equations to adjust for clustering and repeated observations per provider to evaluate the effectiveness of the intervention arms versus usual care. For the inappropriate prescribing outcome, we will use a log link function and binary distributed errors. These models generate the estimated relative risks (RRs) with robust standard errors and are considered to be particularly appropriate when outcomes are common (e.g., incidences of $\geq 10\%$). Because this is a randomized trial, our primary analyses are

planned as unadjusted; however, in secondary analyses, we will adjust for patient age, race/ethnicity, and gender.

Given the nature of the data and how the outcomes are categorized, there will not be missing values for the primary endpoint, as the absence of action is classified as no action by the provider. For the primary analysis, we will include all eligible patients in the denominator who had at least one visit with their primary care provider. In secondary analyses, we will include all eligible patients of those primary care providers in the denominator, regardless of whether the patient visited the provider over the follow-up period.

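### Benzodiazepine and sedative-hypnotic patients need no current order to enter, so patients who had already stopped can count as a reduction in every arm and dilute the primary contrast

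*Combined protocol and SAP*

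**What the plan says.** Section 4.1 admits patients aged 65 or more on this prescribing rule: "Have been prescribed at least 90 pills of benzodiazepine or sedative hypnotic or at least one active orders of at least 90 pills". The limb about active orders then goes on to require a pair of distinct anticholinergics, and the look-back is 180 days. Section 3.2.1 gives the same rule and repeats the verb ("have been prescribed at least 90 pills of benzodiazepine or sedative hypnotic or have been prescribed at least one active orders of"), so the word active belongs to the anticholinergic limb only. Section 4.2 closes the list: "No other exclusion criteria will be used".

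Section 6.2 defines discontinuation as "a) active discontinuation and no subsequent order or b) no order during follow-up". Ordering a taper is the other component. With several classes, "we will classify patients with a reduction for any class as a “reduction” for the composite measure". The only further condition on the primary analysis set is attendance: "Our primary analyses will be within patients who had a visit (telemedicine or in-person) with a study provider after randomization". Section 7.3.1 repeats that condition and adds that "the absence of action is classified as no action by the provider".

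The 180-day window for provider eligibility is stated to end at randomisation. The patient window has no stated end point in either section.

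**The concern.** The primary question is whether the tool leads providers to stop or taper a drug. A benzodiazepine or sedative-hypnotic patient who reached 90 pills early in the window and stopped before randomisation has nothing left to stop. That patient still meets section 4.1. A visit puts the patient in the primary analysis, and if no order follows, limb (b) records a reduction that no provider in the trial brought about. Because one class is enough, a patient who enters on two classes can score on the class already stopped while the other continues.

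Such successes occur in every arm alike. They raise all the rates, shrink the absolute difference and pull the relative risk, which is the reported estimate, towards 1. They also sit badly with the endpoint's justification in section 2 as evidence of changed provider behaviour, and with the statement in section 7.3.1 that absence of action counts as no action.

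**Working it through.** **Inputs.** From section 7.2: usual-care rate 25%, difference 10 points, intra-provider correlation (ICC) 0.1. From sections 3.2.1 and 5.3: about 200 providers in three equal arms, so k = 200/3 = 66.7 per arm. Not given, so assumed: patients per provider m (20 where one value is needed); two-sided alpha 0.05, or 0.025 under Bonferroni; and q, the share of analysed patients who stopped before randomisation and were not re-ordered (5, 10, 20%).

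**1. The plan's own figure.** The effective sample per arm is k·m / [1 + (m − 1)·0.1]. Detecting 25% versus 35% with 80% power needs 329 effective patients per arm at alpha 0.05 and 398 at 0.025 (normal approximation, no continuity correction). Power passes 80% at m = 9 (333 effective, 80.6%) or m = 14 (406 effective, 80.8%) respectively. At m = 20 the effective sample is 1333.3/2.9 = 460, and power is 91.3% or 85.9%. The claim of more than 80% is attainable but cannot be verified without m and alpha.

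**2. Dilution.** If the share q scores as a reduction in both arms, the observed rate is q + (1 − q)·p and the observed difference is (1 − q) times the difference among current users.

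*Reading A: 25% is the rate among current users, who respond at 25% versus 35%.*

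| q | Usual care | Intervention | Difference (points) | RR |
|---|---|---|---|---|
| 0 | 25.0% | 35.0% | 10.0 | 1.40 |
| 5% | 28.8% | 38.3% | 9.5 | 1.33 |
| 10% | 32.5% | 41.5% | 9.0 | 1.28 |
| 20% | 40.0% | 48.0% | 8.0 | 1.20 |

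*Reading B: 25% already includes these patients.* The usual-care rate among current users is (0.25 − q)/(1 − q). A 10-point effect among current users is assumed.

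| q | Usual-care rate, current users | RR, current users | RR, observed |
|---|---|---|---|
| 5% | 21.1% | 1.48 | 1.38 |
| 10% | 16.7% | 1.60 | 1.36 |
| 20% | 6.3% | 2.60 | 1.32 |

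**3. Power if the ICC of 0.1 describes the full analysed set** (m = 20, alpha 0.025). From 85.9%, power falls to 79.2, 72.2 and 58.0% under reading A, and to 82.0, 77.5 and 66.8% under reading B, at q = 5, 10 and 20%.

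**4. Gain from restricting, if the ICC of 0.1 holds among current users** (reading A, m = 20, expected q the same for every provider). Let S = 0.25·0.75 + 0.35·0.65 = 0.415, and let a and b be the diluted rates.

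- Restricted set, with m′ = 20(1 − q): variance = S·[1 + (m′ − 1)·0.1]/m′, and information = 0.10²/variance.
- Full set: variance = [a(1 − a) + b(1 − b) + 19·(1 − q)²·0.1·S]/20, and information = (b − a)²/variance.

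For q = 10%, the restricted variance is 0.415·2.7/18 = 0.06225, giving information 0.1606. The full-set variance is (0.4622 + 0.6387)/20 = 0.05504, giving 0.0081/0.05504 = 0.1472. The ratio is 1.09. For q = 5% it is 0.1635/0.1566 = 1.04, and for q = 20% it is 0.1542/0.1287 = 1.20. The gains are therefore about 4%, 9% and 20%. Power at alpha 0.025 is 84.9% restricted versus 81.3% full at q = 10%, and 83.3% versus 75.4% at q = 20%.

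**5. How many current users the restriction can afford to lose.** Solve 0.01·m″/[0.415·(0.9 + 0.1·m″)] = full-set information. This gives m″ = 16.7 of 19, 14.1 of 18 and 10.3 of 16 at q = 5, 10 and 20%. The gain disappears if about 12%, 22% or 35% of current users are dropped because their recorded order has lapsed.

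**The case against.** **The 25% may already include these patients.** Section 7.2 calls it the rate of the primary outcome, which naturally means limb (b) included. This stands, and reading B is at least as natural as reading A. If the 10-point target also describes the mixed population, the power claim is untouched. The effect needed among current users is then 10/(1 − q) = 10.5, 11.1 or 12.5 points.

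**There is no bias for or against an arm.** A reader might infer that the rule flatters the tool. It does not: status before randomisation cannot depend on the arm, and the same scoring applies everywhere.

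**Not every stopped patient scores.** A reader might treat everyone off the drug at randomisation as a certain success. Patients who restart do not score through limb (b), and those without a visit are outside the primary analysis. So q must mean stopped and not re-ordered, a smaller group. At q = 20%, reading B leaves only 6.3% among current users, which suggests that the top of the range is extreme.

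**The window may not end at randomisation.** If it runs back from an encounter, a prescription written 170 days before randomisation drops out at any visit more than 10 days later. This stands as an ambiguity. The secondary analysis in section 7.3.1, which covers eligible patients with or without a visit, points towards randomisation.

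**The larger information gain.** Treating patients as independent gives gains of 12, 24 and 47% from restriction. The plan's own ICC of 0.1 does not support those figures.

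**Pragmatic breadth, and robustness to a slightly higher baseline rate.** These answer little. The plan already asks for active orders in one class, and the robustness statement in section 7.2 concerns the rate, not a smaller difference.

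**Changing eligibility would change who gets alerts.** This stands, because section 3.2.1 uses one rule for both. It bears on where the change is made.

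**Conclusion.** The gap is real on the text and should be closed, but it is a loss of sensitivity and interpretability, not a threat to validity. If the patient window ends at randomisation, some benzodiazepine and sedative-hypnotic patients with nothing left to stop enter the primary analysis as successes in all arms.

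The documents do not allow the loss to be sized. They give neither q, nor the patients per provider, nor the population behind the 25%, so the tables show assumed values and are not estimates. The direction of the dilution is firm: each 5% of such patients takes 0.5 points off a 10-point effect among current users. The net gain from restricting under clustering is modest and depends on the ICC assumption and on how well recorded orders identify current users. The documents do not support a conclusion that the trial is underpowered.

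**What to change.** 1. Leave the rule that triggers the tool unchanged.
2. In sections 3.2.1 and 4.1, state that the patient 180-day window used for analysis ends at randomisation.
3. In sections 6.2 and 7.3.1, define the primary analysis set as eligible patients with a visit and with current use of a qualifying class at randomisation: an active order, or prescribed supply reaching the randomisation date, not already discontinued. Take this from pre-randomisation EHR data only, identically in all arms.
4. Count limb (b) only for classes in current use at randomisation, and reconcile it with the statement in section 7.3.1 about absence of action.
5. Report the full eligible set, subject to the same visit condition, as a sensitivity analysis. At minimum do the reverse: keep the full set as primary and add the current-use analysis.
6. In section 7.2, state which population the 25% describes, and give the patients per provider and alpha.

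The cost is a few sentences and one more condition in an EHR query, with no change to allocation or data collection. The analysis set becomes somewhat smaller, and some order status will be misclassified. Accepting prescribed supply as well as an active order limits the loss of real users.
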